L	8	763 SOSIP 50 μg + AMC011 SOSIP 50 μg	763 SOSIP 50 μg + AMC011 SOSIP 50 μg	763 SOSIP 50 μg + AMC011 SOSIP 50 μg
М	8	763 SOSIP AMC011 ConM SOSIP Mos3.1 Mos3.2 (each at 20 µg)	763 SOSIP AMC011 ConM SOSIP Mos3.1 Mos3.2 (each at 20 µg)	763 SOSIP AMC011 ConM SOSIP Mos3.1 Mos3.2 (each at 20 μg)

Inclusion Criteria

- 1. Healthy male and female volunteers aged between 18 and 55 years.
- 2. Available for **ALL** follow-up visits for the duration of the study.
- 3. Entered and clearance obtained from The Over volunteering Prevention System (TOPS) database (to avoid impact of any co-administered investigational products or treatments on our outcomes).
- 4. Women of childbearingⁱ potential willing to use a highly effective method of contraceptionⁱⁱ for the duration of the study until a minimum of 12 weeks after the final injection. Periodic abstinence (calendar, symptothermal and post-ovulation methods) and withdrawal are not acceptable methods of contraception.
- 5. Willing and able to give written informed consent.

i A woman will be considered of childbearing potential following menarche and until becoming post-menopausal (no menses for 12 months without an alternative medical cause) unless permanently sterile. Permanent sterilisation methods include hysterectomy, bilateral salpingectomy and bilateral oophorectomy. A post-menopausal state is defined as no menses for 12 months without an alternative medical cause.

- ii The following methods are considered highly effective:
 - combined (estrogen and progestogen containing) hormonal contraception associated with inhibition of ovulation – oral, intravaginal or transdermal;
 - progestogen-only hormonal contraception associated with inhibition of ovulation oral, injectable or implantable
 - intrauterine device (IUD);
 - intrauterine hormone-releasing system (IUS);
 - bilateral tubal occlusion;
 - vasectomised partner, where the vasectomised partner has received medical assessment of the surgical success; and
 - sexual abstinence, defined as refraining from heterosexual intercourse must be the preferred and usual lifestyle of the participant.

Exclusion Criteria

- 1. History of any medical, psychological or other condition, clinically significant laboratory result at screening, or use of any medications which, in the opinion of the investigators, would interfere with the study objectives or volunteers safety.
- 2. Any history of angioedema
- 3. History of urticaria deemed significant by the Chief Investigator
- 4. HIV-1 or HIV-2 antibody positive or indeterminate upon screening, or history of receipt of Env-based HIV immunogens (which would render the volunteers non-naive to the model immunogens).
- 5. Unable to read and/or speak English to a fluency level adequate for the full comprehension of study procedures and consent.

Recruitment & Randomisation

This is a single-blind study with volunteers being randomised into five groups of n=10 (Groups A-E) and eight groups of n=8 (Groups F–M), stratified by gender. Volunteers will be blinded to their treatment regimes, and laboratory teams undertaking immunological analysis will be blinded to group and dosing regimen to prevent in-house analysis bias. The clinical team will remain un-blinded throughout.

Volunteers will be recruited from the general population in London and the surrounding areas by means of paper and electronic advertising. We will also use a Healthy Volunteer database held at the Imperial Clinical Research Facility. We will register volunteers as patients of Imperial College Healthcare NHS Trust before they are consented into the study. Volunteers will also be informed at screening and during the course of the experimental study protocol that the immune challenges will not provide protection against HIV acquisition, and that normal HIV prevention strategies should be maintained.

Once all inclusion/exclusion criteria have been met, eligible volunteers will be enrolled into the study and randomly assigned into one of the nine treatment groups. A study ID will be generated once randomisation has been completed.

Consent

Signed written consent to enter the study must be obtained from each volunteer only after a full explanation has been given, an information leaflet provided, and at least 24-48 hours allowed for consideration. The right of the volunteer to refuse to participate and to withdraw consent at any time from the protocol without giving reasons will be respected.

Model Immunogens

Model immunogens will be obtained from Polymun Scientific, Austria, and stored in temperature controlled conditions, on-site at the Imperial CRF before administration. To ensure reproducibility of results and the highest level of volunteer safety, all immunogens will be manufactured under cGMP, using techniques and specifications applied to vaccines. Recombinant HIV-1 trimeric gp140 Env proteins: ConM SOSIP gp140, ConS UFO gp140, and chemically fixed versions: EDC-ConM SOSIP and EDC-ConS UFO; the mosaic immunogens: Mos3.1, Mos3.2 and Mos3.3; and 763 SOSIP and AMC011, manufactured to EU cGMP quality standards by Polymun Scientific GmbH (Austria) will be mixed with adjuvant: MPLA liposomes manufactured to EU GMP quality standards by Polymun Scientific. All model immunogens will be used at the dosage of 100 μg and will be admixed with 500 μg MPLA formulated in liposomes and administered by intramuscular injection into the left or right deltoid muscle.

Immunogens, adjuvant and dose justification

Env glycoprotein and adjuvant vaccines have been administered without concerning adverse effect in numerous studies worldwide over many years. Extensive safety data for the use of monomeric recombinant gp120 HIV-1 Env glycoprotein vaccines include the large Phase III Vaxgen and RV144 trials - albeit formulated with different adjuvants (Andersson et al. 2011; Su et al. 2000; UNIADS Report 2013). In the RV144 trial, the alum adjuvanted gp120 protein (AIDSVAX B/E) was injected along with ALVAC (canarypox expressing *gag pro* and *Env* genes) after two priming immunisations with ALVAC alone. There were no safety concerns in that trial of over 16,000 healthy volunteers in Thailand.

Previous work by our own group, and others internationally, have used recombinant native HIV-1 Env glycoprotein gp140 in a number of CTIMPs, administered intramuscularly (I.M.) at the dose of 100μg adjuvanted with GLA-AF, an alternative MPLA (non-liposomal) formulation, as well as with other adjuvants such as alum and MF59. The dose of model gp140 immunogens we propose to use in this protocol is therefore identical to the dose of native gp140 (100μg) used in three previous UK clinical trials: MUCOVAC2 (EudraCT 2010-019103-27; Cosgrove CA, 2016); UKHVC Spoke 003 (EudraCT 2012-003277-26; Joseph S, 2017); X001 (EudraCT 2013-001032-22; Kratochvil S, 2017). An intradermal dose of 50ug was acceptable when used in CUTHIVAC002 (EudraCT 2015-001023-23; Cheeseman HM, 2018). The proposed dose of native gp140 was safe, and volunteers made good binding antibody responses to the recombinant gp140, although very limited levels of neutralising antibodies. These previous

studies were performed with a single recombinant HIV-1 clade C trimeric gp140 Env glycoprotein derived from a Chinese viral isolate 97CN54. Additional studies have been performed with gp140 proteins at this dose (100 μ g). A South African subtype C strain TV1 trimeric gp140 protein (100 μ g) combined with MF59 adjuvant was safely administered to 114 volunteers primed with DNA/MVA (Churchyard G, 2016); a purified trimeric gp140 Env derived from the subtype B strain SF162 (100 μ g) in MF59 was administered to 80 subjects with or without DNA priming (Spearman P, 2011); and a subtype D strain UG92005 trimeric gp140 Env (100 μ g) combined with 500 μ g alum was given twice to 9 volunteers (Hurwitz JL, 2008).

To adjuvant the protein this study will use MPLA in liposomal suspension. MPLA has been widely used in liposomal adjuvants for over 20 years (Alving CR, 2011). When given intramuscularly no systemic toxicity has been associated with doses up to 2200 μ g (Fries LF 1992, Heppner DG, 1996, Alving CR, 2011). We have selected a dose of 500 μ g as optimal based on non-human primate immunogenicity studies of gp140, in which there was no toxicity.

We also commissioned GLP-compliant preclinical toxicology testing in rabbits (RTC STUDY NO. A3063, Research Toxicology Centre S.p.A., Italy) to mimic the human challenge studies, in which repeated injections of ConM SOSIP, EDC-ConM SOSIP, ConS UFO and EDC-ConS UFO with MPLA, and of ConM SOSIP and MPLA alone, were administered into the lateral surface of the quadriceps muscle of both legs. No relevant clinical signs were observed, and no reaction at injection sites was observed in any animal treated with the test item during the study. In this model the challenge agents and schedule did not induce adverse effects at systemic or local levels.

Reporting Procedures

Any adverse events will be solicited at each attendance, reviewed by clinicians and recorded. In addition, participants will be asked to complete a symptom diary on the evening after each immunogen challenge, and every evening for 6 days thereafter, and entries will be reviewed by clinicians when they visit the investigator site. Any serious adverse events should be reported to the Sponsor and Research Ethics Committee where in the opinion of the Chief Investigator, the event was: 'related', i.e. resulted from the administration of any of the research procedures; and 'unexpected', i.e. an event that is not listed in the protocol as an expected occurrence. Reports of related and unexpected SAEs should be submitted within 15 days of the Chief Investigator becoming aware of the event, using the NRES SAE form for non-IMP studies.

Possible Adverse Reactions and Adverse Events monitoring

As immediate anaphylaxis may rarely be associated with immunogen challenge (less than 1 in 1 million doses) volunteers will remain in the investigation unit for at least one hour after

immunogen challenge. The symptom diary completed by participants after each immunogen challenge will support the completeness and accuracy of adverse events recording at each attendance.

No serious adverse reactions are anticipated given the wide use of recombinant HIV-1 Env proteins in previous studies, and safe record of using MPLA as a common adjuvant. Various local, non-serious adverse reactions may be anticipated after immunogen challenge, expected to be of short duration, resolving within 1-7 days. These include pain, tenderness, erythema/discolouration, warmth, itching and swelling at the site of injection. Less frequent systemic non-serious adverse reactions associated with immunogen challenge may also occur and include: raised temperature, chills/rigors, myalgia/flu-like general muscle aches, malaise, excess fatigue, headache, nausea/vomiting; and, very rarely abdominal pain, diarrhoea and/or sore throat. These are also anticipated to resolve within a few days (<7 days).

Adverse events associated with lymph node sampling are described in the sub-study protocol, in Appendix 1.

It will be made clear to volunteers that they will be free to withdraw from the study at any time without providing a reason. Any significant, severe adverse reactions will lead to withdrawal of the individual and any serious adverse reactions will terminate the whole study.

Volunteers will be provided with 24 hour emergency contact numbers and clear instructions to call if they feel unwell following immunogen challenge.

Schedule of visits, immunogen challenges, procedures and samples

Volunteers will be screened, have their first immunogen challenge and will be followed for 7 months (Groups J-M), 9 months (Groups F-I) or 13 months (Groups A-E) thereafter. It is expected to take approximately 12 months to enrol 114 volunteers.

Volunteers will be enrolled in the groups described in Table 2 and blood sampling will be carried out at specific time points during the study (see Table 3).

Avoidance of pregnancy during the study

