• These will include: measurement of binding antibodies in serum; assessment of neutralisation breadth using a wider panel of globally circulating HIV strains; measurement of serum antibody function (ADCC, ADCP, FcR dimer binding); measurement of the magnitude and phenotype of B cell (plasmablast and memory B cells) and T cell responses (CD4 and CD8) in peripheral blood mononuclear cells (PBMC). Some endpoints will include only a subset of enrolled volunteers. Paxgene tubes for blood transcriptomics will be collected only from group A (see Table 2) because it is not expected that responses will differ at this level between groups. Blood transcriptomic profiles induced by immunisation will be correlated with the magnitude of induced serum antibody response.

Fine needle aspiration

- In addition, the feasibility and safety of lymph node aspiration will be explored, and immunogen induced germinal centre B and T cell responses will be assessed, in volunteers from groups B-M willing to attend additional visits to have an ultrasound guided fine needle lymph node aspiration from axillary, cervical or inguinal lymph nodes. Fine needle aspiration biopsies will occur in line with the sub-study protocol in Appendix 1.
- This will be optional and participants will be provided with a separate fine needle aspiration information sheet and consent form. The participants will be reviewed by the medical team for any contraindications to fine needle aspiration prior to the procedure being carried out.
- An additional blood sample of 42 ml of peripheral blood will be collected at each fine needle aspiration visit to compare the T- and B-cell populations by flow cytometry and to compare serum neutralising antibody activity.

Statistics and Sample Size

It is difficult to give an estimate of the power of group comparisons using quantitative antibody titre outcomes at this stage as this is dependent on the number of responders, and the large number of experimental parameters in this experimental study. The sample size is based on the previous studies of HIV-1 gp140 immunogens (Joseph S, 2017, Cosgrove CA, 2016, Kratochvil S, 2017, Lewis DJ, 2011). It is not the remit of this exploratory study to recruit a sufficient number of volunteers to be statistically confident about the differences between groups. By the end of this study, 8–10 volunteers will have been exposed to each schedule and this provides confidence around the response/event proportions of 0–100% in Table 1.

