Table 1: Sample Size

Number of "responders"	mber of "responders" Proportion if n=10							
		interval ¹						
0	0%	0 – 31%						
2	20%	3 – 56%						
4	40%	12 – 74%						
6	60%	26 – 88%						
8	80%	44 – 98%						
10	100%	69 – 100%						
Number of	Proportion if n=8	95% confidence						
"responders"		interval ²						
0	0%	0–32%						
1	12.5%	2–47%						
2	25%	7–59%						
3	37.5%	14–69%						
4	50%	22–78%						

5	62.5%	31–86%
6	75%	41–93%
8	100%	68–100%

^{1, 2} Clopper-Pearson or Wilson method (suitable for small sample sizes)

Number (percent) of responders, and median [IQR] and mean (range) of titre responses will be tabulated by group. Group comparisons of titre levels will be conducted via Kruskal-Wallis test or Wilson method suitable for small sample sizes.

Volunteers & Withdrawal Criteria

We will recruit 114 healthy male and females adults into five groups of 10 each (A-E) and eight groups of 8 each (F–M), see Table 2. Recruitment will select potential volunteers who are willing to undergo serial blood draws. Health status will be determined at screening which will comprise a medical history, symptom-directed physical examination, vital signs, urine pregnancy test (women only), HIV screen, and routine safety blood draws (full blood count; renal, liver and bone panels).

Additional volunteers may be enrolled to replace early withdrawals. The reason(s) for withdrawal will be recorded in volunteer's files.

All volunteers are free to withdraw from the study at any time, for any reason, without affecting their future medical care. The PI may decide to withdraw a volunteer if the investigator deems that continuing might compromise the volunteer's wellbeing or interfere with the achievement of the study's objectives.

Table 2: Schedule of immunisations and doses of model immunogens

			Month:	5							
Group	N	0	0 3 6								
			Part 1		Part 2						
Α	10	ConM SOSIP	ConM SOSIP	Mos3.1 + Mos3.2							
		100 μg	100 μg	100 µg	100ug (2x50ug)						
В	10	EDC ConM SOSIP	EDC ConM SOSIP	EDC ConM SOSIP	Mos3.1 + Mos3.2						
		100 μg	100 μg	100 µg	100ug (2x50ug)						
С	10	ConS UFO	ConS UFO	ConS UFO	Mos3.1 + Mos3.2						
		100 μg	100 μg	100 µg	100ug (2x50ug)						
D	10	EDC ConS UFO	EDC ConS UFO	EDC ConS UFO	Mos3.1 + Mos3.2						
		100 μg	100 μg	100 µg	100ug (2x50ug)						
E	10	ConS UFO	ConS UFO	ConM SOSIP	Mos3.1 + Mos3.2						
		100 μg	100 μg	100 μg 100 μg							
			Month								
Group	N	0	2	6							
			Part 1		Part 2						

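### Randomisation is stratified by gender but the titre test named in the protocol is not: conservative, with some loss of power if sex affects titre, and free to correct

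*Protocol*

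**What the plan says.** Under Recruitment & Randomisation, volunteers go into five groups of 10 "and eight groups of n=8 (Groups F–M), stratified by gender". Gender is the only stratification factor named.

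Under Statistics and Sample Size, in the text below Table 1, the primary-outcome titres are to be compared as follows: "Group comparisons of titre levels will be conducted via Kruskal-Wallis test or Wilson method suitable for small sample sizes". No stratum, covariate or significance level is attached. The Wilson method is an interval for a proportion, so Kruskal-Wallis is the only usable titre comparison named. Nothing else in the protocol carries gender into an analysis.

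The same section gives no power ("It is difficult to give an estimate of the power of group comparisons using quantitative antibody titre outcomes at this stage") and limits its aim: "It is not the remit of this exploratory study to recruit a sufficient number of volunteers to be statistically confident" about differences between groups.

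**The concern.** Stratifying by gender makes the groups alike in sex mix, so sex contributes almost nothing to the true differences between group mean ranks. An unstratified Kruskal-Wallis test takes its reference distribution from the ranks of all volunteers together, where any sex difference in titre still counts as noise. The statistic is then judged against too wide a yardstick.

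With 8–10 volunteers per group, sensitivity is scarce. The stated hypothesis is that the prime-boost combinations differ in the neutralising antibodies they induce. A design feature already in place could help detect that, and the named test does not use it.

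**Working it through.** **The plan's own figures.** Group sizes add up: 5 × 10 + 8 × 8 = 114. Table 1's intervals reproduce as Clopper-Pearson for n = 10 and Wilson for n = 8 in 13 of 14 rows; 8/10 gives 44–97% against the printed 44–98%. The protocol gives no power, level, sex ratio or sex difference for the titre test, so there is no figure of its own to reproduce on this point.

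**Inputs.** From the protocol: groups of 10 (A–E) and 8 (F–M), stratification by gender, Kruskal-Wallis. Assumed: 5% level, normal log titres with equal SD, sex balanced within every group, and a sex difference of δ within-sex SDs.

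**Approximate size by formula.** With a proportion p of one sex in each group, the pooled variance is about 1 + p(1 − p)δ² times the within-sex variance. For five groups the 5% cut-off is 9.488 (chi-square, 4 df), and P(χ²₄ > x) = e^(−x/2)(1 + x/2). The actual type I error is therefore about P(χ²₄ > 9.488 × [1 + p(1 − p)δ²]).

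- δ = 0.5, p = 0.5: factor 1.0625, x = 10.08, giving 3.9%.
- δ = 0.8, p = 0.5: factor 1.16, x = 11.01, giving 2.6%.
- δ = 1.0, p = 0.5: factor 1.25, x = 11.86, giving 1.8%.
- δ = 0.8, p = 0.2: factor 1.1024, x = 10.46, giving 3.3%.

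**Simulation, five groups of 10, 5:5 sex split.** Type I error is from 30,000 trials per cell. Power is for two groups shifted by 1 SD, comparing the plain test at its chi-square cut-off with the same statistic permuted within sex.

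| Sex effect (SD) | Type I error, plain | Power, plain | Power, permuted within sex |
|---|---|---|---|
| 0 | 4.3% | 71% | 72% |
| 0.5 | 3.4% | 68% | 73% |
| 0.8 | 2.3% | 63% | 74% |
| 1.0 | 1.5% | 55% | 72% |

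The 4.3% in the first row is the usual small-sample value for the chi-square cut-off. At 4,000 trials, power near 70% has a standard error of √(0.7 × 0.3 / 4,000) = 0.7 points, so the 1-point difference with no sex effect is noise. Repeat runs at 0.8 SD put the plain test's power at 60–63% and its type I error at 2–3%.

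**Sensitivity** (one group shifted by 1.2 SD, 0.8 SD sex effect, plain test against a sex-stratified rank test):

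- Five groups of 10, 5:5 split: 57% v 66%.
- Five groups of 10, 20% of one sex: 61% v 66%, with plain type I error 2.9%.
- Four groups of 8, 4:4 split: 46% v 54%.
- Five groups of 10, about half of titres at a floor: 57% v 65%.
- Sex not balanced by group: plain type I error stays at 4.0–4.6%, so there is no distortion to correct.

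At a 0.25 SD sex effect the plain and stratified tests are practically equal in the five-group setting (66% v 66%).

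**The case against.** The strongest reply is that one outline sentence in a protocol does not exclude a stratified analysis, and that covariates are commonly settled in the SAP, which is not shown here. Stratifying for balance and then using an unstratified rank test is common and valid. The protocol also disclaims confidence about group differences, so it makes no promise that a loss of power could break.

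Much of this stands. It makes the point minor and rules out several stronger readings that a reader might infer:

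- That any sex difference costs power. At 0.25 SD or less the loss is practically nil. In a comparison of two groups of 10, a van Elteren-type test overtakes the plain test only at about 0.8 SD.
- That the results would be invalid. The error is conservative; false positives are not inflated.
- That confidence intervals are affected. Kruskal-Wallis yields none, and Table 1's intervals are for proportions within a single group.
- That a stated level or power is missed. Neither is given for this test.

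What does not stand is the claim that this is only an SAP omission. The protocol itself names the primary-outcome comparison ("Group comparisons of titre levels will be conducted via Kruskal-Wallis test") and names it without the design factor. An SAP that added sex would be changing the stated test.

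**Conclusion.** The mismatch is real and minor. If sex is balanced across groups and affects titre, the named test is conservative and gives up some power. For five groups of 10 with a 5:5 split, a 5% level and two groups shifted by 1 SD, the loss is nil with no sex effect, about 5 points at 0.5 SD and about 10 points at 0.8 SD, with type I error there of about 2–3%. An unequal sex split makes it smaller. The sex effect, sex ratio, level and shift are all assumptions, since the protocol gives none of them. A reader should not infer that the planned comparison is invalid or that a promised power is missed. The case for changing it is only that the improvement is free.

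**What to change.** In the text below Table 1, keep the Kruskal-Wallis statistic and add that its p-value comes from permuting group labels within sex, among groups randomised together. State the number of permutations and the seed. In the simulations this restored the 5% level and cost no power when sex had no effect. Because the statistic still ranks the titres as measured, ties at the assay floor need no special handling.

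Do not align titres by subtracting sex means before ranking. That splits ties at the floor by sex, and with many titres at the floor it gave 53% power against 57% for plain ranks, both permuted within sex. A linear model of log10 titre with group and sex can serve as a supporting analysis where few titres are at the floor.

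The randomised set must be clear first. The same section lists 13 groups (A–M) and then says volunteers are "randomly assigned into one of the nine treatment groups". These need to be reconciled, because they decide which labels may be exchanged.

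The cost is a sentence or two of analysis text and a few lines of code. No new data are needed, because sex is already recorded for randomisation.

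### Does the word nine in the allocation sentence leave it unclear how many groups volunteers are randomised to?

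*Protocol*

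**What the plan says.** The first paragraph of Recruitment & Randomisation says that volunteers are "randomised into five groups of n=10 (Groups A-E) and eight groups of n=8 (Groups F–M), stratified by gender". The third paragraph of that section covers the step after eligibility is confirmed, when the volunteer is enrolled and "randomly assigned into one of the nine treatment groups".

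Two other sections describe the same structure:

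- Volunteers & Withdrawal Criteria gives a total of 114 and splits it as "five groups of 10 each (A-E) and eight groups of 8 each (F–M".
- Schedule of visits, immunogen challenges, procedures and samples: volunteers "will be followed for 7 months (Groups J-M), 9 months (Groups F-I) or 13 months (Groups A-E) thereafter". The same paragraph adds: "It is expected to take approximately 12 months to enrol 114 volunteers".

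The background text gives the scientific reason for Groups J–M and says that their responses will be compared with those in Groups A–I. Table 3 has a separate visit schedule for J–M.

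**The concern.** Thirteen and nine cannot both describe one randomisation. Nine is also exactly the number of groups in A–I (five in A–E and four in F–I), so the sentence reads as if it belonged to a design without J–M. The document does not say why the word stands there, and the match with A–I is only an observation.

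The sentence also sits in a sensitive place, because it describes how an individual volunteer is allocated. The protocol intends to set J–M beside A–I. If J–M had been filled outside the randomisation, that comparison would lose the protection that randomisation gives against differences between the volunteers in each block. A reader who saw only this sentence could wonder whether that was so. An author who copied it into the trial report would misstate the number of groups.

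**Working it through.** **Inputs**

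- Groups A–E: 5 groups of 10 (Recruitment & Randomisation; Volunteers & Withdrawal Criteria).
- Groups F–M: 8 groups of 8 (same two sections).
- Stated total: 114 (Volunteers & Withdrawal Criteria; Schedule of visits).
- Groups with a stated follow-up period: A–E, F–I and J–M (Schedule of visits).
- Group count in the allocation sentence: 9.

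**Step 1. Reproduce the stated total.** N = (groups of 10) × 10 + (groups of 8) × 8 = 5 × 10 + 8 × 8 = 50 + 64 = 114. This matches the protocol exactly, with 5 + 8 = 13 groups.

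**Step 2. Try nine groups, read as A–I.** N = 5 × 10 + 4 × 8 = 50 + 32 = 82. The shortfall is 114 − 82 = 32, which is the size of J–M (4 × 8).

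**Step 3. Try any nine groups.** With every group at 8 or 10, the smallest total is 9 × 8 = 72 and the largest is 9 × 10 = 90. Neither end of the range, nor anything between, reaches 114.

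**Step 4. Count the groups that are followed up.** A–E, F–I and J–M give 5 + 4 + 4 = 13.

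**Step 5. Look for anything that depends on the word nine.**

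| Element of the plan | Rests on | Uses nine? |
|---|---|---|
| Total recruited | group sizes in the text | no |
| Confidence intervals in Table 1 | n = 10 or n = 8 per group | no |
| Stratification by gender | opening sentence of Recruitment & Randomisation | no |
| Summaries and Kruskal-Wallis comparison of titres | groups as listed | no |
| First safety review by the Data Safety Monitoring Committee | about half of all immunogen challenges given | no |
| Follow-up and visits | Table 3, by block A–E, F–I, J–M | no |

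The protocol gives no power calculation, significance level or multiplicity rule that takes the number of groups as an input. The word enters no formula.

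**The case for a change.** The best case for a correction is that this is current body text, in an intact sentence, and it is wrong as it stands. It is a misstatement in the protocol, so a separate analysis plan would not excuse it. Replacing one word would cost nothing, and a description of randomisation should not contradict itself. All of that is true.

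A harder form of the objection is that the word might signal staged allocation, with A–I opened first and J–M later. The three blocks have different schedules and follow-up periods. The protocol's section on restarting after a pause speaks of volunteers already enrolled when COVID-19 interrupted participation, so this text was in force after recruitment had begun. If allocation was staged, putting thirteen in place of nine would not describe it accurately either, and the comparison of J–M with A–I would need to be read with that in mind.

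The mismatch itself stands. The staging reading has no support in the document: the section opens by randomising across A–M without stages, and the allocation sentence covers all eligible volunteers without naming a subset. Different schedules by block do not show that the blocks opened at different times. Any doubt about concurrent allocation would come from how the trial was run, and this one word is not evidence on that.

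**Conclusion.** The inconsistency is genuine: thirteen groups in one paragraph and nine in another, a difference of four. It is a clerical slip, and no change to the plan follows. The group letters, sizes and stratification factor are stated correctly two paragraphs earlier in the same section and agree with the recruitment section, the follow-up periods and the total of 114. Only thirteen groups reproduce that total; nine give 82 if read as A–I and at most 90 on any reading. A statistician who builds the allocation list or the analysis dataset would work from the listed groups and would not leave out J–M.

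The effect on sample size, precision, comparisons and safety review is nil. Tidying the word when the text is next edited would do no harm, but it would not alter design, conduct or inference. This conclusion assumes that the opening sentence of Recruitment & Randomisation governs, which every other section at hand supports, and that allocation was not staged, since the protocol describes no stages.
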